7. INVESTIGATIONAL PLAN

7.1. Overall Study Design and Flow Chart

This is a Phase 2a, double-blind, placebo-controlled, multi-center study to assess the efficacy and safety of a repeat-dose regimen of IRL201104 in participants with active EoE. A study diagram is provided in [Figure 1](#).

Eligible participants will undergo an up-to-6-week screening period to stabilize current therapy, confirm diagnosis by histologic assessment, and other eligibility criteria. Participant compliance to DSQ reporting will be assessed for at least 2 consecutive weeks prior to randomization.

At the end of the screening period, eligible participants will be randomized in a 1:1:1 ratio to one of 3 arms, as displayed in Figure 1:

[figure not shown]
- Arm 1: IRL201104 4 mg IV with endoscopy and esophageal biopsy 2 weeks after last dose (Week 4).
- Arm2: IRL201104 8 mg IV with endoscopy and esophageal biopsy 2 weeks after last dose (Week 4).
- Arm 3: Placebo IV with endoscopy and esophageal biopsy 2 weeks after last dose (Week 4).

Participants will receive IRL201104 (4 mg or 8 mg IV) or placebo on Days 0, 7, and 14 (3 total doses over 14 days). Participants will be evaluated for clinical and histologic responses at Week 4. All participants will be assessed for safety and continued biomarker sampling through Week 8.

The Schedule of Events for the study is provided in [Table 3](#).

The total duration of the study for a given participant is up to 14 weeks.

Figure 1: Study RVLO 121-04 Diagram

D = day; EGD = esophagogastrroduodenoscopy; EOS = End of Study; ICF = informed consent form; IV = intravenous; R = randomization; WK = week

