8. SELECTION AND WITHDRAWAL OF PARTICIPANTS

8.1. Participant Inclusion Criteria

A participant must meet the following criteria to be eligible for inclusion in the study:

1. Age 18 to 75 years old, inclusive, at the time of signing the informed consent form.
2. Documented diagnosis of EoE by endoscopy prior to screening.
Note: Must include a demonstration of intraepithelial eosinophilic infiltration (peak cell count ≥ 15 eos/hpf [400 \times]) from esophageal biopsy specimens from endoscopy.
3. History (by participant report) of on average at least 2 episodes of dysphagia (with intake of solids off anti-inflammatory therapy) per week in the 4 weeks prior to screening, and on average at least 2 episodes of documented dysphagia per week during any 2 consecutive weeks (qualifying period) between screening and baseline; dysphagia is defined as trouble swallowing solid food, or having solid food stick, by participant report; and completed the DSQ on $\geq 70\%$ of days during the qualifying period prior to baseline (Visit 1).
4. Must remain on a stabilized diet for at least 6 weeks prior to screening and during the course of the study; stable diet is defined as no initiation of single or multiple elimination diets or reintroduction of previously eliminated food groups.
5. Must be willing and able to continue any dietary therapy and/or medical regimens (including gastric acid suppression) in effect at the screening visit. There should be no change to these regimens during the study participation.
6. Willing and able to comply with all clinic visits and study-related procedures.
7. Able to understand and complete study-related questionnaires.
8. Provide signed informed consent.
9. Esophagogastroduodenoscopy (EGD) with photographs performed at screening (qualifying EGD), with a demonstration of intraepithelial eosinophilic infiltration (peak cell count ≥ 15 eos/hpf) in at least 2 of the 3 biopsied esophageal regions (proximal, mid, or distal).

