11.2. Dysphagia Symptom Questionnaire

The DSQ is used to measure the frequency and intensity of dysphagia. The DSQ scores can range from 0 to 84, with a lower score indicating less frequent or less severe dysphagia (Dellon 2013).

The questionnaire will be completed by participants daily. Each evening before bedtime, participants will be asked to indicate if they experienced dysphagia symptoms (eg, food passing slowly or food sticking) during that day. Participants must have experienced dysphagia (response of “yes” to Question 2 on DSQ) on a minimum of 2 days total and completed the DSQ on $\geq 70\%$ of days in at least 2 consecutive weeks (qualifying period) prior to the baseline visit (Visit 1). Participants must fill out the DSQ at least 5 or more days during a given week in order to be compliant.

Calculations will be performed on daily ePRO entries from the qualifying period prior to baseline, and prior to each study visit during the treatment and follow-up periods. The DSQ score for the secondary endpoints will be calculated by summing the scores of responses to Questions 2 and 3 only. Questions 1 and 4 will be excluded from the DSQ score.

DSQ score for 14-day period =

$$\frac{(\text{Sum of points from questions 2+3 in the daily DSQ with non-missing data over the interval being reported}) \times 14}{\text{Number of diaries reported with non-missing data over the interval being reported}}$$

Number of diaries reported with non-missing data over the interval being reported

For each DSQ calculation, the sum of the specified question(s) from each reported daily diary with non-missing data over the interval being reported will be obtained, dividing this by the number of reported daily diaries with non-missing data in that same interval. This result will then be multiplied by the interval. This normalizes each DSQ sum over the interval. For the DSQ score, if a response of “No” is recorded for Question 2, the DSQ score will be set to zero for that day. The DSQ calculations during the interval being reported prior to the baseline visit will be defined as the baseline DSQ evaluation. For each 14-day period, at least 8 reported diaries are needed to effectuate a DSQ calculation for that period. If at least 8 diaries are not available, the DSQ result for that 14-day period will be set to missing.

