11.5. Patient Global Impression of Severity

The PGI-S is a PRO measure that uses a verbal rating scale of severity. The PGI-S uses a recall period that aligns with the assessment period used for calculating DSQ endpoint scores (ie, DSQ endpoints are based on 14-day scores, and the PGI-S is administered on the last day of the 14-day assessment period. The PGI-S instructs participants to recall over the past 14 days, such that the anchor covers the same 14-day period as the 14-day DSQ endpoint score).

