4 DEFINITIONS AND DERIVATIONS

Baseline: Baseline is defined as the last non-missing value (whether from scheduled or unscheduled visit) prior to the first study drug administration.

Change from Baseline: The change from baseline values at all post-baseline visits will be calculated by subtracting the baseline value from the corresponding post-baseline value.

Change from Baseline = Post baseline value - Baseline value.

Percent reduction: The percent reduction is the ratio of the reduction in the post-baseline value to its baseline value multiplied by 100.

$$\text{Percent reduction} = \frac{\text{Post Baseline value} - \text{Baseline value}}{\text{Baseline value}} \times 100$$

End of the Study: The end of the study is defined as the final follow-up visit by the last participant. If the study is terminated prematurely, the study ends when the sponsor notifies the investigator in writing that the study has finished, or when the last participant attends the final follow-up visit, whichever is later.

Study Day: This is the number of days from the date of the first study drug administration to a target date:

$$\begin{aligned} \text{Study Day} &= (\text{Target Date} - \text{Date of the first study drug administration}) + 1 \\ &\quad (\text{If target date is greater than or equal to the date of the first study drug administration}) \\ &\quad \text{or} \\ \text{Study Day} &= (\text{Target Date} - \text{Date of the first study drug administration}) \\ &\quad (\text{If target date is less than date of the first study drug administration.}) \end{aligned}$$

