7.7.2 Analysis of Secondary Endpoint(s)

For the secondary endpoints, continuous variables will be summarized using the descriptive statistics (n, mean, standard deviation, median, minimum, and maximum) for each observed measurement and change from baseline at each time point by treatment group while categorical variables will be summarized using the counts and percentages as applicable. The FAS will be used for this evaluation. Analysis will also be done using the SAS.

Dysphagia Symptom Questionnaire (DSQ)

The DSQ is used to measure the frequency and intensity of dysphagia. The DSQ scores can range from 0 to 84, with a lower score indicating less frequent or less severe dysphagia.

The questionnaire will be completed by participants daily. Each evening before bedtime, participants will be asked to indicate if they experienced dysphagia symptoms (eg, food passing slowly or food sticking) during that day. Participants must have experienced dysphagia (response of “yes” to Question 2 on DSQ) on a minimum of 2 days total and completed the DSQ on $\geq 70\%$ of days in at least 2 consecutive weeks (qualifying period) prior to the baseline visit (Visit 1). Participants must fill out the DSQ at least 5 or more days during a given week in order to be compliant. Calculations will be performed on daily ePRO entries from the qualifying period prior to baseline, and prior to each study visit during the treatment and follow-up periods. The DSQ score for the secondary endpoints will be calculated by summing the scores of responses to Questions 2 and 3 only. Questions 1 and 4 will be excluded from the DSQ score.

$$\text{DSQ score for 14-day period} = \frac{(\text{Sum of points from questions 2+3 in the daily DSQ with non-missing data over the interval being reported}) \times 14}{\text{Number of diaries reported with non-missing data over the interval being reported}}$$

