For each DSQ calculation, the sum of the specified question(s) from each reported daily diary with non-missing data over the interval being reported will be obtained, dividing this by the number of reported daily diaries with non-missing data in that same interval. This result will then be multiplied by the interval. This normalizes each DSQ sum over the interval. For the DSQ score, if a response of “No” is recorded for Question 2, the DSQ score will be set to zero for that day. The DSQ calculations during the interval being reported prior to the baseline visit will be defined as the baseline DSQ evaluation. For each 14-day period, at least 8 reported diaries are needed to effectuate a DSQ calculation for that period. If at least 8 diaries are not available, the DSQ result for that 14-day period will be set to missing.

The absolute change in DSQ score from baseline will be summarized as the n, mean, standard deviation, median, minimum, and maximum by treatment group.

Additionally, exploratory endpoint analysis of absolute days without dysphagia will be summarized as the n, mean, standard deviation, median, minimum, and maximum by treatment group. Absolute days without dysphagia will be obtained through a counting process of the number of DSQ records between baseline and Week 8 that the participant reports DSQ question #2 as “No.”

Esophageal intraepithelial Eosinophil

The proportion of participants achieving peak esophageal intraepithelial eosinophil count of < 15 eos/hpf (Week 4) will be summarized using frequency and percentage.

Also, percent reduction in peak esophageal intraepithelial eosinophil count (eos/hpf) (Week 4) will be summarized as the n, mean, standard deviation, median, minimum, and maximum by treatment group.

Also, exploratory endpoint analysis will be performed for esophageal intraepithelial eosinophil. The proportion of participants achieving peak esophageal intraepithelial eosinophil count of ≤ 1 and ≤ 6 eos/hpf (400 \times) at Week 4 will be summarized separately using frequency and percentage.

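### The 14 days behind the baseline DSQ score are not fixed: one rule uses a symptom-selected fortnight from anywhere in screening, others point to the last 14 days before dosing.

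*Protocol*

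**What the plan says.** Criterion 3 (protocol 8.1) requires "on average at least 2 episodes of documented dysphagia per week", met "during any 2 consecutive weeks (qualifying period) between screening and baseline", with the diary completed on at least 70% of days in that period. Protocol 7.1 sets the length of screening: "Eligible participants will undergo an up-to-6-week screening period".

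Four statements bear on which diaries form the DSQ baseline:

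- SAP 7.7.2, repeating protocol 11.2: "Calculations will be performed on daily ePRO entries from the qualifying period prior to baseline".
- The same sections, a little later: "The DSQ calculations during the interval being reported prior to the baseline visit will be defined as the baseline DSQ evaluation". No first or last day is given.
- SAP section 4, for all variables and with no DSQ exception: "Baseline is defined as the last non-missing value (whether from scheduled or unscheduled visit) prior to the first study drug administration".
- Protocol 11.5 and SAP 7.7.3: PGI-S is given on the last day of the DSQ assessment period, so that "the anchor covers the same 14-day period as the 14-day DSQ endpoint score". The schedule of events first administers PGI-S at Visit 1.

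Protocol 11.2 and SAP 7.7.2 state the symptom requirement differently, as dysphagia "on a minimum of 2 days total". They also describe the qualifying period as 2 or more consecutive weeks, so its length is open too. A 14-day score needs at least 8 diaries. DSQ change is summarized by arm without formal testing, and inference rests on clinical evaluation of the summaries (protocol 15.1, SAP section 3).

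**The concern.** A participant may satisfy criterion 3 early in screening and be dosed weeks later. The first rule then takes baseline from the early fortnight, while the SAP section 4 rule and the PGI-S text take it from the last one. No rule says which fortnight counts if several qualify. The clause giving the SAP precedence over the protocol does not help, because the competing rules are all inside the SAP. Two programmers could follow the plan and derive different values for a secondary endpoint.

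There is also a selection effect. A qualifying fortnight is accepted because its symptoms reached a threshold. If those same diaries become the baseline, the later score will tend to be lower even when nothing has changed. In a study with about 12 participants per arm and only descriptive summaries, such a fall in an active arm could be taken for symptom benefit.

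**Working it through.** The documents give no expected untreated DSQ change, so there is no figure to reproduce. The planned 36 participants rest on no power calculation, and the point does not depend on that number.

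**Arithmetic from the documents**

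- Possible 14-day windows in a full 6-week screening: 42 − 14 + 1 = 29.
- Longest gap from the end of a qualifying window to Visit 1: 42 − 14 = 28 days.
- Criterion 3 threshold: 2 episodes per week × 2 weeks = 4 episodes. The other wording asks for 2 days. Four episodes could fall on 2 days, so the two can coexist, but they select differently.
- Largest daily score implied by the 0 to 84 range: 84 / 14 = 6 points.
- Diaries needed to qualify: 0.70 × 14 = 9.8, so 10. Diaries needed for a score: 8.

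**Simulation with no treatment effect**

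Assumptions, none from the documents: six screening weeks and four later weeks; windows taken as pairs of calendar weeks (5 in screening); outcome in weeks 3 and 4 after baseline; mean daily chance of dysphagia 0.30 to 0.55; between-person Beta distribution with concentration 4 to 6; weekly within-person SD 0 or 0.7 on the logit scale with autocorrelation 0.5; complete diaries; one episode per symptomatic day; 120,000 simulated people per scenario.

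The table gives the mean untreated change in symptomatic days per 14 days. Columns A, B, C and E use a threshold of 4 days, column D a threshold of 2.

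| Mean, concentration, weekly SD | A: baseline = first qualifying window | B: baseline = last 14 days, eligibility on any window | C: baseline and eligibility both on last 14 days | D: as A, 2-day threshold | E: enrolled on any window but under 4 days in last 14 |
|---|---|---|---|---|---|
| 0.30, 6, 0 | −0.79 | −0.12 | −0.65 | −0.28 | 28% |
| 0.30, 6, 0.7 | −1.06 | −0.21 | −1.04 | −0.37 | 30% |
| 0.40, 4, 0 | −0.51 | −0.08 | −0.41 | −0.18 | 18% |
| 0.40, 4, 0.7 | −0.73 | −0.13 | −0.70 | −0.25 | 21% |
| 0.55, 5, 0.7 | −0.36 | −0.04 | −0.39 | −0.10 | 11% |

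Approximate conversion to DSQ points, at an assumed 2 to 6 points per symptomatic day:

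- A: 0.36 × 2 = 0.7 to 1.06 × 6 = 6.4 points of apparent improvement.
- B: 0.04 × 2 = 0.1 to 0.21 × 6 = 1.3 points.
- C: 0.39 × 2 = 0.8 to 1.04 × 6 = 6.2 points.
- D: 0.10 × 2 = 0.2 to 0.37 × 6 = 2.2 points.

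Columns A and C are about equal, so the fall comes from using the same diaries to select and to measure. A floating window is not needed to produce it. Column B separates the two uses and removes most of the fall.

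Between two arms of 12, with the first qualifying window as baseline, the mean difference in untreated change was about 0 (−0.05 to 0.02 days at either threshold).

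**The case against.** The strongest reply is that the plan can be read consistently. The reported interval before the baseline visit, the PGI-S alignment and the SAP section 4 rule all fit the last 14 days. This stands in part. A reader might infer that the DSQ rules flatly contradict each other, but they diverge only when the qualifying fortnight is not the last one. The reply does not remove the sentence that sends the calculation to the qualifying period, nor does it name the days.

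A reader might also infer that allowing any fortnight is what creates the drift. Column C shows otherwise: testing eligibility on the last 14 days as well would leave the fall about as large. Moving the eligibility window is therefore not the remedy.

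A third tempting reading is that the worst fortnight becomes baseline, which would give a much larger fall. No section says or implies that, so no such figure belongs in the assessment.

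Nor do the documents support a claim of bias in active versus placebo. Allocation is randomized, the rule applies to all arms, and the arms are summarized side by side. The DSQ objective is itself worded as exploring a relationship.

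Two further objections stand. The sizes rest on assumed parameters and shrink under the 2-day threshold. Forty-two diary days is also a maximum: screening may be shorter, and the schedule lists handset issue at both Visit −1 and Visit 0, which leaves fewer candidate windows.

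**Conclusion.** The concern holds as an undefined baseline window with a real consequence. When the qualifying fortnight ends before the last 14 days, one stated rule gives an older baseline chosen for its symptoms, and the other statements give a different one. With the first qualifying fortnight as baseline, the untreated within-arm improvement is roughly 0.7 to 6.4 points on the 0 to 84 scale. With the last 14 days and eligibility left as it is, it is roughly 0.1 to 1.3. Both ranges assume a threshold of 4 symptomatic days; at 2 days the first falls to about 0.2 to 2.2. The direction is secure whenever selection and baseline share diaries, but the sizes depend on the simulation's assumptions.

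The damage is to how each arm's change is read, to the match between DSQ and PGI-S at baseline, and to whether the endpoint can be derived the same way twice. The expected comparison between arms is unaffected. This is worth correcting, and the correction is cheap.

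**What to change.** In SAP sections 4 and 7.7.2, and in protocol 11.2, define baseline DSQ as the 14-day score for the 14 days ending the day before first dose, with at least 8 diaries, whichever fortnight established eligibility. Ending the day before dosing matters because the diary is filled in each evening, so the Day 0 entry follows the first dose. Leave the eligibility window unchanged. Present and read each active arm's change beside the placebo change. The two statements of the symptom threshold should also be reconciled.

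The cost is a sentence or two in each place and no new data collection, since diaries run daily from issue. The downside is that the 70% completion rule covers only the qualifying period. Someone who qualified early may have fewer than 8 diaries in the last 14 days, and the SAP then sets the score to missing without imputation. With about 12 per arm, even a few losses are noticeable. Report how many baselines are missing by arm, and add a sensitivity summary using the qualifying-period score, with a stated rule for which fortnight is used when several qualify.

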8.2. Participant Exclusion Criteria

A participant who meets any of the following criteria will be ineligible to participate in this study:

1. Prior participation in an IRL201104 clinical study.
2. Has any current disease of the gastrointestinal tract (aside from EoE) that may impact, in the investigator's opinion, the patient's EoE disease status. This includes, but not limited to: eosinophilic gastritis, eosinophilic enteritis, eosinophilic duodenitis, eosinophilic colitis, or proctitis; inflammatory bowel disease; or celiac disease.

3. Has other causes of esophageal eosinophilia or the following diseases: hypereosinophilic syndromes, Churg-Strauss vasculitis (eosinophilic granulomatosis with polyangiitis), or peripheral blood absolute eosinophil count of > 1500 eosinophils/ μ L.
4. Has presence of oral or esophageal mucosal infection of any type.
5. Has any condition affecting the esophageal mucosa or altering esophageal motility other than EoE.
6. History of achalasia, active *Helicobacter pylori* infection, Crohn's disease, ulcerative colitis, celiac disease, and prior esophageal surgery (with the exception of a surgical repair of an EoE complication).
7. Any esophageal stricture unable to be passed with a standard, diagnostic, adult (9 to 10 mm) upper endoscope or any critical esophageal stricture that requires dilation at screening; or dilation within 2 months prior to screening.
8. On a pure liquid diet or any mouth or dental condition that prevents normal eating.
9. Has initiated, discontinued, or changed dosage regimen of PPIs within the 4 weeks prior to the qualifying EGD, between the qualifying EGD and baseline visit (Visit 1), or anticipates changes in the use of PPI during the study. PPI must remain constant throughout the study.
10. History of bleeding disorders or esophageal varices.
11. Use of anticoagulants within 2 weeks prior to screening. Participants should not stop these agents solely to become eligible for entry into this study.
12. Treatment with an investigational drug within 2 months or within 5 half-lives (if known), whichever is longer, prior to screening.
13. Use of systemic corticosteroids within 3 months or swallowed topical corticosteroids within 6 weeks prior to screening.
14. Treatment with oral immunotherapy (OIT) within 6 months prior to screening.
15. Allergen immunotherapy (sublingual immunotherapy [SLIT] and/or subcutaneous immunotherapy [SCIT]), unless on a stable dose for at least 1 year prior to screening.
16. The following treatments within 3 months before the screening visit, or any condition that, in the opinion of the investigator, is likely to require such treatment(s) during the study:
Systemic immunosuppressive/immunomodulating drugs (eg, omalizumab, cyclosporine, mycophenolate-mofetil, interferon [IFN] γ , Janus kinase inhibitors, azathioprine, methotrexate, and other biologics that are ongoing [eg, dupilumab, benralizumab, mepolizumab, or vedolizumab]).
17. Diagnosed with active parasitic infection; or suspected parasitic infection, unless clinical and (if necessary) laboratory assessments have ruled out active infection before randomization.
18. Chronic or acute infection requiring treatment with systemic antibiotics, antivirals, or antifungals within 1 month prior to screening.

19. Use of oral antibiotics/anti-infectives within 2 weeks prior to screening.
20. Known or suspected immunosuppression, including history of invasive opportunistic infections (eg, tuberculosis, non-tuberculous mycobacterial infections, histoplasmosis, listeriosis, coccidioidomycosis, pneumocystosis, aspergillosis) despite infection resolution, or otherwise recurrent infections of abnormal frequency, or prolonged infections suggesting an immunocompromised status, as judged by the investigator.
21. Known history of human immunodeficiency virus (HIV) infection.
22. Positive or indeterminate hepatitis B surface antigen (HBsAg) or hepatitis C antibody at screening.
23. Moderate or severe renal impairment (eGFR <60 mL/min/1.73 m²) or end stage renal disease.
24. Elevated transaminases (alanine aminotransferase [ALT] and/or aspartate aminotransferase [AST]) > 3 times the upper limit of normal (ULN) at screening.
25. History of malignancy within 5 years prior to screening, except completely treated in situ carcinoma of the cervix and completely treated and resolved nonmetastatic squamous or basal cell carcinoma of the skin.
26. Any other medical or psychological condition including relevant laboratory abnormalities at screening that, in the opinion of the investigator, suggest a new and/or insufficiently understood disease, may present an unreasonable risk to the participant as a result of his/her participation in this clinical study, may make the participant's participation unreliable, or may interfere with study assessments. The specific justification for participants excluded under this criterion will be noted in study documents (eg, chart notes, electronic case report form). These may include participant-reported alcohol or drug abuse and severe concomitant illness(es).
27. Planned or anticipated use of any prohibited medications and procedures (as described in the exclusion criteria) during study treatment.
28. Treatment with a live (attenuated) vaccine within 3 months prior to screening and/or treatment of a killed vaccine within 30 days prior to screening, until the end of the study with the exception of a coronavirus disease of 2019 (COVID-19) vaccine, as described in Section 9.2.1.
29. Pregnant or breastfeeding women, or women planning to become pregnant or breastfeed during the study.
30. Women unwilling to use adequate birth control, if of reproductive potential* and sexually active. Adequate birth control is defined as agreement to consistently practice an effective and accepted method of contraception throughout the duration of the study and for 30 days after the last dose of study treatment. These include: hormonal contraceptives, intrauterine device, or double barrier contraception (ie, condom and diaphragm), or male partner with documented vasectomy.

*For females, menopause is defined as at least 12 consecutive months without menses; to include laboratory confirmation of post-menopausal status (ie, a follicle stimulating hormone (FSH) of 2.25 U/mL must be documented). Hysterectomy, bilateral

oophorectomy, or bilateral tubal ligation must be documented, as applicable; if documented, women with these conditions are not required to use additional contraception.

